2.2.12.3 Exploratory Endpoints

- Time to response by Week 8. A Kaplan-Meier lifetable will be constructed using nominal visits. A Wilcoxon-Gehan test will be used to compare all treatments; p-values will also be computed for each of the three treatment pairs for the primary endpoint using the FAS population. This will be a graph.
- Probability of being in response (PBIR) between Weeks 2 and 8. The PBIR will be computed as a descriptive statistic for the primary endpoint using the FAS population. Each visit will be equally weighted in this analysis. This will be a graph.

- Sustained efficacy between Weeks 8 and 10. This analysis will be endpoint-specific. Binary endpoints will be evaluated using logistic regression (PROC LOGISTIC) controlling for baseline IGA score and baseline AD severity while continuous endpoints will be analyzed using PROC GLM controlling for the same factors. A shift table will be created presenting the number and frequencies of subjects in response and the shift from Week 8 to Week 10 for the primary endpoint analysis for both the FAS and PPS populations.
- Change from baseline in the Dermatology Life Quality Index (DLQI) score in treated population compared to vehicle population at Week 2, 4, 6, 8 and 10 and from Week 8 to Week 10 and change from baseline to subject's last treatment visit. These analyses will be done using PROC MIXED similar to the code described above.

DLQI is a set of 10 questions, scored 0=Not at all, 1=A little, 2=A lot, or 3=Very much, or 0=Not relevant, except for Questions 1 and 2 that do not include a response of 'Not Relevant'. Missing responses are assigned '0'. The DLQI total score is calculated by summing the score of each question resulting in a maximum of 30 and a minimum of 0. The higher the score, the more quality of life is impaired. This scoring will be done by the data management group and provided to CTDS in the SDTM datasets.

Mean DLQI will be computed as the Total DLQI divided by the number of questions with non-missing responses. The scoring instructions for DLQI specify that if 2 or more questions are not answered, then the questionnaire will not be scored; this approach is not taken here with Mean DLQI computed instead. Summary statistics for Total DLQI and Mean DLQI will be presented. The analysis of change from baseline in Mean DLQI will be performed the same as the analysis of change from baseline in EASI, with appropriate changes in the variables for change from baseline and Mean DLQI at baseline.

Summary statistics as continuous data and change from baseline will be presented by treatment group and visit for the totals for the 4 sub-scales:

Symptoms and feelings	Questions 1 and 2
Daily Activities	Questions 3 and 4
Leisure	Questions 5 and 6
Personal relationships	Questions 8 and 9

- Change from baseline in the Patient Orientated Eczema Measure (POEM) score in treated population compared to vehicle population at Week 2, 4, 6, 8 and 10 and from Week 8 to Week 10 and change from baseline to subject's last treatment visit. These analyses will be done using PROC MIXED similar to the code described above.

POEM is a set of 7 questions regarding the frequency of conditions related to eczema, with responses of 0 = no days. 1 = 1-2 days, 2 = 3-4 days, 3 = 5-6 days, or 4 = every day. The sum of the scores for the 7 questions is the Total POEM.

Mean POEM is the Total POEM divided by the number of questions with non-missing responses. The scoring instructions for POEM specify that if response to one question is missing, the response for that question will be equated to 0, and if the responses to more than one question are missing, then the questionnaire is not scored; this approach is not taken here with Mean POEM for questions with non-missing responses computed instead. The analysis of change from baseline in Mean POEM will be performed the same as the analysis of change from baseline in EASI, with appropriate changes in the variables for change from baseline and Mean POEM at baseline.

Summary statistics (counts and frequencies) will be presented by treatment group and visit for categories based on Total POEM of:

Clear or almost clear = 0 to 2;
Mild eczema = 3 to 7;
Moderate eczema = 8 to 16;
Severe eczema = 17 to 24;
Very severe = 25 to 28.

Shift tables presenting the number and frequency of subjects in each eczema severity category at Week 8 and last treatment visit and Week 8 to Week 10 will be presented by treatment group.

- Change from baseline in the Patient Global Impression of Severity (PGI-S) score in treated population compared to vehicle population at Week 2, 4, 6, 8 and 10 and from Week 8 to Week 10 and change from baseline to subject's last treatment visit. These analyses will be done using PROC MIXED similar to the code described above.

The categories for the PGI-S are: normal, mild, moderate or severe. A Shift table will be created presenting the number and frequencies of

subjects in each category and the shift from the follow-up visit to baseline.

- Change from baseline in the Patient Global Impression of Change (PGI-C) score in treated population compared to vehicle population at Week 2, 4, 6, 8 and 10 and from Week 8 to Week 10 and change from baseline to subject's last treatment visit. PGI-C is captured at the follow-up visits and is a 7 –point scale assessing the overall status of the patient since the start of the study with responses of 1=very much improved, 2=much improved, 3=minimally improved, 4= no change, 5=minimally worse, 6= much worse and 7=very much worse. Summary statistics (count and frequencies) will be presented by treatment group and visit for the status categories. A shift table presenting the number and frequency of subjects in each category at Week 8 to Week 10 will be presented by treatment group.
- Determination of AD biomarkers in treated population compared to vehicle population at Baseline/Day 0 and Week8/Early Termination (samples to be retained for the potential analysis at a later date). Details of these analyses will be described in a separate document and the analyses will not be included with the analyses described herein. The method for controlling the Type I error rate is provided in Section 2.2.12.4.

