#### 9.1.5 Dermatology Life Quality Index (DLQI) Questionnaire

The effect of AD on patient quality of life will be self-assessed by the patient at baseline/Visit 2, Week 2/Visit 3, Week 4/Visit 4, Week 6/Visit 5, Week 8/Visit 6/ET and follow up Week 10/Visit 7 using the DLQI (Appendix 6) developed by Finlay and Khan (1994)

DLQI has a maximum value of thirty based on the patients response to ten questions scored according to the following scale:

- Very much = 3
- A lot = 2
- A little = 1
- Not at all = 0
- Not relevant = 0
- Question unanswered = 0
- Question 7: "prevented work or studying" = 3

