**Please check you have answered EVERY question. Thank you.**

## 15.7 Appendix 7: Patient Orientated Eczema Measure

Patient ID #: \_\_\_\_\_ - \_\_\_\_\_

Patient Initials: \_\_\_\_\_

Visit Day: \_\_\_\_\_

Visit Date (dd-mmm-yyyy): \_\_\_\_\_

**Please circle one response for each of the seven questions below about your eczema. Please leave blank any questions you feel unable to answer.**

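### Blank DLQI and POEM items add nothing to the totals, with no limit on their number, so the descriptive tables can show incomplete forms only as equal or milder

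*SAP*

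**What the plan says.** **DLQI.** SAP 2.2.12.3 states "Missing responses are assigned '0" and defines the total: "The DLQI total score is calculated by summing the score of each question resulting in a maximum of 30 and a minimum of 0". Protocol 9.1.5 has the same item rule, "Question unanswered = 0". Neither document limits the number of blanks. Scoring is done before the data reach the analysis group: "This scoring will be done by the data management group and provided to CTDS in the SDTM datasets". The SAP then adds a second score: "Mean DLQI will be computed as the Total DLQI divided by the number of questions with non-missing responses". It notes that under the scoring instructions "if 2 or more questions are not answered, then the questionnaire will not be scored; this approach is not taken here with Mean DLQI computed" in its place.

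**POEM.** The SAP states "The sum of the scores for the 7 questions is the Total POEM" and gives no value for a blank item. Mean POEM is that total over the number of items answered. The SAP cites the POEM instructions (one blank counts as 0; with more than one the form is not scored) and sets them aside in favour of the mean. The patient form in Protocol Appendix 7 says "Please leave blank any questions you feel unable to answer".

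**Outputs.** The change-from-baseline models use Mean DLQI and Mean POEM. These endpoints are steps 7 and 8 in Table 2 of SAP 2.2.12.4. Total DLQI and totals for four two-item DLQI sub-scales are summarised descriptively. POEM severity categories, and the shift tables built on them, use Total POEM.

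**The concern.** The SAP's reason for dropping the instruments' limits is that a mean of answered items replaces the unscored form. That reason covers the means only. The totals, sub-scales, categories and shift tables are still produced, and they lose the safeguard without gaining a substitute. Blanks are foreseeable for POEM, because the form invites them.

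Two things are at stake. The tables can understate disease severity and quality-of-life impairment for incomplete forms. One form can also carry two inconsistent results: a mean that implies one severity and a category that states a lower one.

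A smaller matter concerns data transfer. In the DLQI coding a 0 can mean no effect, not relevant, or unanswered. If zero-filled scores arrive without a flag, the number of answered items cannot be recovered from them, and Mean DLQI needs that number as its denominator.

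**Working it through.** **Inputs**
- DLQI: 10 items scored 0 to 3, blank = 0 (SAP 2.2.12.3; Protocol 9.1.5).
- POEM: 7 items scored 0 to 4 (SAP 2.2.12.3; Protocol 9.1.6). Categories on the total: 0–2 clear or almost clear, 3–7 mild, 8–16 moderate, 17–24 severe, 25–28 very severe.
- Blank rate: not in the documents. Shown below for 0, 1, 2, 3 and 5 blanks.

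**Stated ranges reproduced.** 10 × 3 = 30 and 7 × 4 = 28, as the documents give.

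**Value of a blank POEM item.** Mean POEM = Total / number answered. For this to be the mean of the answered items, Total must be the sum over answered items, so a blank adds nothing. This is an inference. Otherwise Total POEM is undefined whenever an item is blank.

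**Direction.** Complete-form total = reported total + the scores that the blank items would have had. Those scores are 0 or more, so the reported total can only equal or fall below the complete-form total. With m blanks the shortfall is at most 3m for DLQI and 4m for POEM.

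**Size, when every item would have had the same score**

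| Blanks | DLQI total (items = 2) | Total / answered | Total / 10 | POEM total (items = 3) | Mean POEM | POEM total (items = 4) |
|---|---|---|---|---|---|---|
| 0 | 20 | 2.0 | 2.0 | 21 severe | 3.0 | 28 very severe |
| 1 | 18 | 2.0 | 1.8 | 18 severe | 3.0 | 24 severe |
| 2 | 16 | 2.0 | 1.6 | 15 moderate | 3.0 | 20 severe |
| 3 | 14 | 2.0 | 1.4 | 12 moderate | 3.0 | 16 moderate |
| 5 | 10 | 2.0 | 1.0 | 6 mild | 3.0 | 8 moderate |

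With two POEM blanks and answered items at 3, the total is 5 × 3 = 15 (moderate). The mean of 3.0 corresponds to 3.0 × 7 = 21 (severe).

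**Sub-scales.** Two items at 2 give 2 + 2 = 4. With one blank the sub-scale total is 2 + 0 = 2, half the value. The SAP defines no mean for the sub-scales.

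**Category shifts.** If all POEM response patterns were equally likely (an assumption for scale only), 22%, 42% and 64% of forms would fall to a lower category with 1, 2 and 3 blanks.

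**Means.** A zero adds nothing to the numerator, so Total / answered is exactly the mean of the answered items and does not move with the number of blanks. The Total / 10 column shows what Mean DLQI would become if zero-filled blanks were counted as answered: 1.6 instead of 2.0 with two blanks.

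**The case against.** The best defence is that this is a disclosed scoring choice for exploratory endpoints. The SAP quotes the limits, says openly that it departs from them, and shows Mean DLQI beside Total DLQI. Zero for an unanswered DLQI item is also specified in the protocol. This stands as far as it goes, but it gives no reason for leaving the totals and categories unprotected.

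A reader might infer more than the documents support:

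- *That the mean's denominator conflicts with zero-filling.* It does not. As shown above, the two rules together give the plain mean of the answered items.
- *That the formal tests at steps 7 and 8 are biased.* The SAP models the means, which zero-filling leaves alone. Mean DLQI would be wrong only if the count of answered items were lost in transfer. The SAP's formula requires that count, and nothing says that blanks are overwritten.
- *That the SAP states a zero for POEM blanks.* Its zero rule sits in the DLQI paragraph. It mentions a zero for POEM only in describing the instructions that it does not follow.
- *That the treatment comparison is biased.* The understatement is in score level. A blank at baseline understates improvement and a later blank overstates it. In a randomised double-blind trial the documents give no reason to expect more blanks in one arm.

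**Conclusion.** The point holds for the descriptive outputs: Total DLQI, the four DLQI sub-scale totals, and the POEM categories and shift tables. For DLQI it rests on stated rules. For POEM it rests on the inference from the definition of Mean POEM; on any other reading the total lacks a rule for blanks and still needs one.

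The error runs one way for each form, by up to 3 points per blank DLQI item and 4 per blank POEM item. Two blanks are enough to move a POEM form from severe to moderate. How many forms are affected cannot be said, because the documents give no blank rate, and the direction between arms is unknown. The modelled means stand, provided that blanks stay identifiable in the DLQI data. This is a minor point that is cheap to correct, best settled before database lock.

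**What to change.** In SAP 2.2.12.3, apply to the totals the limits that the SAP already cites:

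1. Set Total DLQI, Total POEM, the POEM category and the shift-table entry to missing when two or more items are blank. Count a single blank as 0, which agrees with Protocol 9.1.5 and with the cited POEM rule.
2. Set a two-item DLQI sub-scale total to missing when either item is blank. This is a new rule, so state it explicitly.
3. Require data management to supply item-level responses with blanks flagged as missing, distinct from a scored 0, so that the Mean DLQI denominator is correct.

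Scaling the mean up to a total (× 10 or × 7) is not proposed. It would depart from the protocol's zero for an unanswered DLQI item and from the cited POEM rule for one blank.

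The cost is SAP wording, a small change to the derivations and one line in the data-transfer specification. Incomplete forms drop out of the descriptive tables; these are probably few, but the number is unknown. SAP Appendix A 4.2 already bases percentages on non-missing data. Some understatement remains with a single blank: POEM items all at 4 with one blank still total 24 (severe), not 28. The means would still have no minimum number of answered items; this change leaves that choice as it is.

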2.2.12.4 Controlling Type I error

Dunnett's test will be used to provide for simultaneous comparisons of each DS107 dose vs. vehicle by allowing two-sided $p=0.026$ per dose comparison.

No multiplicity adjustment is necessary for the primary and co-primary endpoints as the Type I error rate will not be affected because both must be met for study success. A hierarchical testing sequence methodology will be applied to the second and exploratory endpoints in order to control the overall type 1 error. Table 2 provides the order of testing for each active dose group compared to the vehicle group for the secondary and exploratory efficacy endpoints; these will each be global tests across all post-baseline outcomes excluding Week 10. Each of these tests will be at the 0.05 significance level. A test will be considered statistically significant only if the corresponding test has a p -value <0.05 and all previous tests (as determined by the testing order defined in Table 2) have a p -value <0.05 .

Table 2. Hierarchical Testing Sequence for Secondary and Exploratory Endpoints

Testing Order	Endpoint	Efficacy Endpoint
1	Secondary	Change in NRS from baseline
2	Secondary	Proportion achieving a reduction of at least 2.7 points in NRS
3	Secondary	Change in EASI from baseline
4	Secondary	Proportion achieving an IGA score of 0 or 1 and a decrease of at least 2 points in IGA
5	Secondary	Proportion achieving a decrease of at least 2 points in IGA
6	Secondary	Change in IGA from baseline
7	Exploratory	Change in DLQI from baseline
8	Exploratory	Change in POEM from baseline
9	Exploratory	Change in PGI-S from baseline
10	Exploratory	Change in PGI-C from baseline

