STATISTICAL ANALYSIS	
The primary analysis will be conducted in the full analysis set (FAS) population.
 
Final analyses will be conducted using exact two-sided 97.4% confidence intervals for each DS107 dose minus vehicle difference; this strategy (Dunnett's procedure) preserves the overall two-sided 5% Type I error. This allows either DS dose (1% and 5%) to be separately tested.
 
A hierarchical testing sequence will be adopted, giving a pre-defined testing order for multiple efficacy endpoints.
 
A generalised linear mixed model (GLMM) will be used to separately analyze the continuous primary and co-primary efficacy endpoints at Week 8. The models will include Treatment Arm as a factor and respective baseline value as a covariate, with the treatment-by-visit interaction term as a random effect to account for missing data at Week 8. In addition, IGA-response will be analysed using a longitudinal mixed model for binary outcomes (GENMOD).
 
Change from baseline for secondary and exploratory endpoints (IGA, DLQI, POEM, PGI-S and PGI-C) will be analysed using mixed model with repeated measures (MMRM) with Treatment Arm as a factor and respective baseline value as a covariate, with the treatment-by-visit interaction term as a random effect to account for missing data at Week 8.
 
Sensitivity analyses will be performed to assess the robustness of the Missing at Random (MAR) assumptions that support the GLMM methods above for imputing missing data.

SPONSOR:	DS Biopharma

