2.2.8 Statistical Hypotheses

The original null hypothesis (H_0) for each analysis is the equality of the means for the three treatment groups. A global test was to be performed across all three treatment groups. The test will still be performed

The revised primary focus will be the separate comparisons of the two DS107 concentrations vs. vehicle control using a Dunnett’s correction (two-sided 97.4% confidence intervals and two-sided $p=0.026$) to reach statistical significance. The null hypotheses are the pairwise comparisons of the equality of the two DS107 concentrations vs. vehicle. Dunnett’s procedure will be used to adjust for the multiple comparisons. The overall 5% Type I error rate is controlled for by the Dunnett’s correction for multiple comparisons.

Testing between the two active groups will be considered as descriptive statistics.

All statistical testing will be two-sided; global tests will be performed at the 0.05 level while all pairwise DS107 comparisons vs vehicle will be performed at the 0.026 level.

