2.2.9 Sample Size Justification

The sample size for the topical DS107 Phase IIb study was informed from the post-hoc analysis of the Phase IIa study. NRS and EASI will be the primary and co-primary efficacy endpoints. The positive efficacy data over 4 weeks showed no sign of a plateau and suggests further improvements may be observed at Week 8. Dunnett's procedure will be used to allow simultaneous comparisons of each DS dose concentration vs. vehicle control.

The sample size was estimated from the Phase IIa results at Week 4/exit; the mean improvement and corresponding standard deviation for vehicle subjects were used to perform the following calculations. As shown below, 100 patients per treatment arm (300 patients in total) will be required to detect mean advantages of 3.03 units for NRS (10-point scale) and 6.6 units for EASI favoring DS107 vs. vehicle. This assumes a two-sided test with 80% power conducted at the 5% overall significance level with a Dunnett's adjustment for multiple doses.

Table 1. Sample Size Calculation

Two group Satterthwaite t-test: No Difference (unequal variances) (equal n's)		
	NRS	EASI
Overall Dunnett's Type I Error	0.026	0.026
1 or 2 sided test?	2	2
Target DS107 Mean Reduction, μ_1	3.030	6.600
Expected Vehicle Mean Reduction, μ_2	1.810	4.000
Mean Difference Goal, $\mu_1 - \mu_2$	1.220	2.600
Phase 2a DS107 Standard Deviation, σ_1	2.490	4.450
Phase 2a Vehicle Standard Deviation, σ_2	3.040	7.110
Power (%)	80	80
n per group	100	100

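### The fixed 0.026 test for each dose is valid, but a step-down across the two doses would give more power to confirm the second dose within the stated 5% familywise error

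*SAP*

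**What the plan says.** SAP 2.2.8 requires that "all pairwise DS107 comparisons vs vehicle will be performed at the 0.026 level", with global three-arm tests at 0.05. SAP 2.1 repeats the 0.026 level, and SAP 2.2.12.4 states that Dunnett's "test will be used to provide for simultaneous comparisons of each DS107 dose vs. vehicle by allowing two-sided" p = 0.026 for each comparison. The protocol synopsis, under statistical analysis, states: "Final analyses will be conducted using exact two-sided 97.4% confidence intervals for each DS107 dose minus vehicle difference". It adds: "This allows either DS dose (1% and 5%) to be separately tested".

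The sample size (SAP 2.2.9 Table 1, Protocol 12.3 Table 6) is set for one dose against vehicle: "This assumes a two-sided test with 80% power conducted at the 5% overall significance level with a" Dunnett adjustment. SAP 2.2.12.1 requires success on both NRS and EASI before the drug is called effective.

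The sequential testing rules in Protocol 12.9.2 and SAP 2.2.12.4 order the endpoints. Neither lets one dose be tested at a relaxed level once the other has passed on the primary endpoints. Neither document gives the power to confirm both doses or a correlation between NRS and EASI.

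**The concern.** Protocol section 3 describes a dose-finding study, so the verdict on each dose matters. With only two doses, once one has been shown effective at a level that protects the family, a single null hypothesis is left. By the closed testing principle that hypothesis can be tested at the full 0.05. Holding it at 0.026 makes a truly effective second dose harder to confirm. The co-primary rule adds to this, because the second dose must clear the stricter threshold on two endpoints. What is at stake is power for the second dose. Error control and the chance that the trial succeeds on at least one dose are not at stake.

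**Working it through.** **Inputs** (SAP 2.2.9 Table 1; the same in Protocol Table 6): n = 100 per arm, 1:1:1. Differences 1.22 (NRS) and 2.60 (EASI). SDs 2.49 and 4.45 on DS107, 3.04 and 7.11 on vehicle. Two-sided 0.026. The NRS-EASI correlation r is not in the documents, so it is assumed and varied from 0 to 0.7.

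**1. Reproduce the plan's figure.** Standard error = √[(σ₁² + σ₂²)/n].
- NRS: √[(6.200 + 9.242)/100] = 0.393; 1.22/0.393 = 3.10.
- EASI: √[(19.80 + 50.55)/100] = 0.839; 2.60/0.839 = 3.10.

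With the Satterthwaite t-test at 0.026, power at n = 100 is 80.5% (NRS) and 80.2% (EASI). The n for 80% power is 99 and 100. The plan's 100 per group is confirmed.

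**2. Why a step-down is allowed.** A dose is null if it lacks an effect on NRS or on EASI. Let p_dose = max(p_NRS, p_EASI); this is a valid 0.05 test of that null. The step-down rule tests the smaller p_dose at 0.026 and, only if that is significant, the other at 0.05. The first threshold is unchanged, so every single-step rejection is kept and some are added.

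**3. Power with both doses at the planned effect.** Simulation with a shared vehicle arm and the Table 1 means and SDs, giving the probability that both doses are confirmed:

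| Rule | Single-step | Step-down | Gain (points) |
|---|---|---|---|
| NRS alone | 70.6% | 78.9% | 8.3 |
| EASI alone | 72.0% | 79.8% | 7.8 |
| NRS and EASI, r = 0 | 50.8% | 62.6% | 11.8 |
| NRS and EASI, r = 0.3 | 54.2% | 65.2% | 11.0 |
| NRS and EASI, r = 0.5 | 56.9% | 67.4% | 10.4 |
| NRS and EASI, r = 0.7 | 60.1% | 70.0% | 9.8 |

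(Gains are from unrounded values. A normal approximation at r = 0.3 gives 55% to 66%.) At r = 0.3 the chance that a given dose wins on both endpoints rises from 67.2% to 72.7%. The chance of at least one successful dose is 80.2% under either rule.

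**4. Power with other true effects** (NRS and EASI both required, r = 0.5; chance that both doses are confirmed):
- One dose at half the planned effect, the other at full effect: +6.6 points.
- Both at 60%: +5.5. Both at 90%: +10.9. Both at 120%: +6.5.

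At r = 0.3 the half-effect and 60% cases give about 6 and 5 points.

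**5. Familywise error.**
- *One dose null, the other strongly effective:* 2.6% with single-step, 5.0% with step-down.
- *Both null on the same endpoint:* any error needs a rejection at the first step, so the two rules agree. The correlation between the dose statistics is σ₂²/(σ₁² + σ₂²), which is 9.242/15.442 = 0.60 for NRS and 50.55/70.35 = 0.72 for EASI. The error at 0.026 is 4.7% and 4.4%. With equal variances (correlation 0.5) it is 4.8%.
- *Null on different endpoints, other effects large:* the two deciding statistics are independent at r = 0. At 0.026 the error is 1 − 0.974² = 5.13%, the same for both rules. At 0.025 it is 1 − 0.975² = 4.94%. At 0.0271 it is 1 − 0.9729² = 5.35%.

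**The case against.** The strongest reply is that nothing here is wrong. Fixed 0.026 per dose is a standard, prespecified procedure. The trial is sized per dose, that target reproduces, and no section sets a power target for confirming both. All of this stands.

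Single-step testing also has advantages. Its tests agree exactly with the simultaneous 97.4% intervals on which the synopsis bases the final analysis. It also holds the error for a lone null dose at 2.6%. Both are given up under step-down. The second loss stays within the stated 5% target. The first is a matter of presentation, but a real one: a dose could be declared effective while its 97.4% interval includes zero.

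A reader might also infer that the first threshold can be raised. Dunnett's level for three equal-variance arms is about 0.027, slightly above 0.026. That inference fails for the co-primary rule, because two doses that are null on different endpoints would push familywise error to about 5.35%. It also assumes a correlation of 0.5 between the dose statistics, which the planning SDs do not give.

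Finally, the size of the gain is conditional. It rests on the true effects and on a correlation that the documents do not supply.

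**Conclusion.** The single-step rule is valid and leaves some efficiency unused. If both doses have the planned effect and each must win on NRS and EASI, step-down adds about 10 to 12 points to the chance of confirming both, for correlations from 0 to 0.7. It adds about 8 points on one endpoint, and about 5 to 6 if one dose has half the effect or both have 60% of it. These figures assume 100 evaluable patients per arm, the planning SDs, and that the same dose must win on both endpoints. An interim change in sample size (SAP 2.2.10) would alter the figures but not the logic.

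Two stronger readings are not supported. The plan's multiplicity control is not broken by the missing step-down: the small excess at 0.026 (up to 5.13%) occurs only when the doses are null on different, nearly uncorrelated endpoints, and step-down neither creates nor removes it. Nor is the trial short of its own power target: the per-dose 80% is met on each endpoint, and step-down does not change the chance of at least one successful dose. This is an optional improvement.

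**What to change.** Before unblinding, and preferably before interim results are available to those drafting the change:

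1. Define p_dose as the larger of the Week 8 NRS and EASI p-values against vehicle.
2. Test the dose with the smaller p_dose at 0.026. Alternatively use 0.025, which makes the rule Holm's procedure and holds familywise error at or below 5% in every configuration. That costs about 0.4 points of per-endpoint power at the first step (NRS 80.5% to 80.0%, EASI 80.2% to 79.8%). With 0.025 the rule no longer keeps every rejection made at 0.026. Do not raise this step to 0.0271.
3. Only if that dose is significant, test the other at 0.05.
4. Keep the 97.4% intervals for reporting, and state that the test decides and the interval is descriptive for the second dose.

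Amend SAP 2.1, 2.2.8 and 2.2.12.4. The statistical section of the protocol synopsis must change too, because it bases the final analysis on the 97.4% intervals. Check that the interim sample-size wording (SAP section 1, Study Design, and 2.2.10), which refers to a two-sided 2.6% error per dose, still reads consistently.

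The cost is wording only, with no added patients, visits or data. There are two downsides. The second dose's 97.4% interval may include zero when its p lies between 0.026 and 0.05. The error for a single null dose rises from 2.6% to 5% when the other dose is effective.

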The primary focus will be the separate comparisons of the two DS107 concentrations vs. vehicle control using a Dunnett's correction (two-sided $p=0.026$) to reach statistical significance supported by the two-sided p-values and the two-sided 97.4% confidence intervals (Dunnett's procedure). Comparisons between the two active groups will be considered to be descriptive statistics.

The following summary statistics will be reported for continuous data: number of subjects, mean, standard deviation, median, minimum and maximum. For categorical data, the number and percentage of subjects within each treatment group will be reported.

Baseline values will be defined as the last non-missing measurement prior to dosing with study drug (where baseline record flag='Y' in datasets), unless otherwise specified. Change from baseline will be defined as the post-baseline visit value minus the baseline or previous value unless otherwise specified.

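### The 0.026 level (97.4% intervals) attributed to Dunnett's procedure is a slightly conservative figure; the Dunnett level for two doses against one vehicle arm at 1:1:1 is about 0.0270 (97.3%)

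*SAP*

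**What the plan says.** Two DS107 concentrations are each compared with one vehicle arm, randomised 1:1:1 with about 100 patients per arm. SAP 2.2.12.4 says that Dunnett's test handles the two comparisons "by allowing two-sided $p=0.026$ per dose comparison". SAP 2.2.8 defines the tests: "The null hypotheses are the pairwise comparisons of the equality of the two DS107 concentrations vs. vehicle". The same section says that "all pairwise DS107 comparisons vs vehicle will be performed at the 0.026 level" and, of the overall error, "The overall 5% Type I error rate is controlled for by" Dunnett's correction. SAP 2.1 gives the matching intervals as "two-sided 97.4% confidence intervals (Dunnett's procedure").

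The protocol synopsis plans "exact two-sided 97.4% confidence intervals for each DS107 dose minus vehicle difference", names this Dunnett's procedure, and says that it "preserves the overall two-sided 5% Type I error".

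The figure 0.026 is also the alpha in both sample size tables (protocol 12.3, Table 6; SAP 2.2.9, Table 1), where the row is labelled "Overall Dunnett's Type I Error". It is the level for the interim sample size update as well (SAP section 1, Study Design; SAP 2.2.10). Neither document shows how 0.026 was obtained.

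**The concern.** Once the number of comparisons, the allocation ratio and the overall level are fixed, Dunnett's procedure determines the per-comparison level, apart from a slight dependence on degrees of freedom. A plan that names the method and also fixes a number should have the two agree. Here they do not. An analyst who runs Dunnett as named and one who applies 0.026 would disagree on any unadjusted p-value between 0.026 and about 0.027. The number is the threshold for each dose on both NRS and EASI, so a pre-specified plan should permit only one answer.

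The table label adds a smaller inconsistency. It calls 0.026 the overall error, while the text above the table sets the overall level at 5%.

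**Working it through.** **Inputs.** Two comparisons with a shared vehicle arm (SAP 2.2.8); 1:1:1 allocation (SAP 2.2.11.1); 100 per arm, and the planning differences and SDs (SAP 2.2.9, Table 1); overall two-sided 5% (SAP 2.2.8 and protocol synopsis). Assumption: a common variance. The PROC MIXED code in SAP 2.2.12.1 requests no arm-specific variances.

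**Reproducing the plan's sample size at 0.026.** Satterthwaite t-test, with SE = √((σ₁² + σ₂²)/n) and noncentrality = difference/SE.
- NRS: SE = √((2.49² + 3.04²)/100) = 0.393; noncentrality = 1.22/0.393 = 3.10; df about 191; power 80.5%. The smallest n for 80% is 99.
- EASI: SE = √((4.45² + 7.11²)/100) = 0.839; noncentrality = 2.60/0.839 = 3.10; df about 166; power 80.2%. The smallest n for 80% is 100.

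So the stated 100 per arm is confirmed at 0.026.

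**Dunnett level.**
- Each contrast has variance 2σ²/n. The covariance through the shared vehicle mean is σ²/n, so the correlation is (σ²/n)/(2σ²/n) = 0.5.
- Solve P(max(|T₁|, |T₂|) > c) = 0.05 by numerical integration; the level is then 2·P(T > c).

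| Error df | c | Per-comparison level | Familywise error at 0.026 | Familywise error at 0.027 |
|---|---|---|---|---|
| infinite | 2.2121 | 0.02696 | 4.83% | 5.01% |
| 297 (300 − 3) | 2.2227 | 0.02699 | 4.82% | 5.00% |
| 20 | 2.3787 | 0.02745 | 4.74% | 4.92% |

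A simulation of 4 million draws at 297 df gave 4.81% at 0.026.

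**Could 0.026 come from elsewhere?** Bonferroni gives 0.0250 and Šidák 0.0253. Fewer df only raise the Dunnett level. A Dunnett level of 0.026 would need a contrast correlation of about 0.34, which 1:1:1 does not give under a common variance. Cutting 0.02696 to three decimals gives 0.026, whereas rounding to nearest gives 0.027.

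**Consequences.**
- Interval width: the multiplier at 0.026 and 297 df is 2.2374, and 2.2374/2.2227 = 1.0066, about 0.7% wider.
- Power at n = 100, moving from 0.026 to 0.027: NRS 80.46% to 80.87%; EASI 80.24% to 80.66%. Both gain about 0.4 points.
- Patients per arm for 80% power: NRS 99 to 98; EASI 100 to 99.

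**Sensitivity to unequal variances.** If arm-specific standard errors were used with the planning SDs, the correlation would be σ₂²/(σ₁² + σ₂²).
- NRS: 9.2416/15.4417 = 0.598; level 0.0279; familywise error at 0.026 of 4.7%.
- EASI: 50.5521/70.3546 = 0.719; level 0.0296; familywise error at 0.026 of 4.4%.

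These use the normal approximation. In both cases 0.026 is still conservative.

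**The case against.** The strongest reply is that nothing the plan says about error control is false. To preserve or control 5% is to respect an upper bound, and 4.82% does so. The 97.4% intervals cover jointly with at least 95% probability under the same assumptions. This stands. A reader might infer from the mismatch that the 5% claim fails, but the discrepancy runs the other way.

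Second, 0.026 may be a deliberate rounding down. At the planned size it is the largest three-decimal level that keeps the error within 5%, since a fixed 0.0270 gives 5.002% at 297 df and 5.008% at infinite df. This is plausible, but the documents do not say it, and the synopsis calls the intervals exact. It does mean that writing 0.0270 in place of 0.026 is not a clean repair.

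Third, a reader might take 4.8% as the trial's overall false-positive rate. The documents do not support that. SAP 2.2.12.1 and 2.2.12.4 require both NRS and EASI to succeed. If both nulls hold, simulation puts the chance that some dose passes both at 0.1% to 1.4%, for assumed endpoint correlations of 0 to 0.7. The 4.8% is approached only if the other endpoint is almost certain to succeed. The interim analysis is also left out of the figure.

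Fourth, the remark about interval width applies to the intervals described in the text. The SAP code sets alpha=0.052 on the MODEL statement and no alpha on LSMEANS, so it does not request 97.4% intervals. That conflict matters more, but it is a separate point.

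On the table label, the sentence above each table gives the overall level as 5%, so few readers would be misled. The label is still wrong.

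**Conclusion.** The attribution is inexact: 0.026 with 97.4% intervals is not what Dunnett's procedure gives for this design, which is about 0.0270 with 97.3%. The effect is minor and in the safe direction. Per endpoint, familywise error is about 4.82%, interval width is up by about 0.7%, and about 0.4 points of power per comparison, or one patient per arm, are given up. This rests on a common variance, equal arms, about 297 error df (more df hardly change it) and no allowance for the interim analysis. Neither the 5% control claim nor the sample size of 100 per arm is called into question. Low priority.

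**What to change.** Choose one of two options.

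1. Judge each dose by its Dunnett-adjusted p-value at 0.05, with 95% Dunnett simultaneous intervals, for the two Week 8 dose-versus-vehicle contrasts only. ADJUST=DUNNETT on the planned LSMEANS trt*visit statement will not do this, because the adjustment would run over treatment-by-visit cells, and the MODEL statement has no such interaction. The model and a Week 8 contrast must be written out.
2. Keep 0.026 and 97.4%, and describe them as a conservative rounding of the Dunnett level (about 0.0270, with single-endpoint familywise error about 4.8%), dropping the word exact.

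Under either option, relabel the alpha row in protocol Table 6 and SAP Table 1 as the per-comparison level (overall 5%). Then align the protocol synopsis and SAP section 1 (Study Design), 2.1, 2.2.8, 2.2.10, 2.2.12.1 and 2.2.12.4.

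Option 2 costs wording only. Option 1 also needs the model code and contrast rewritten. Neither needs further data or patients.
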